Secondary Aim/Objective: *(if applicable)*

A secondary aim of the study is to examine the effects of vortioxetine vs placebo on overall functioning and quality of life.

Primary Endpoint(s):

The primary efficacy measure is the number of binge eating days per week based on clinician interview and confirmation of identified Binge eating episodes in self-reported Binge eating diaries. The primary efficacy end point is the change from baseline to week 12 on the log-transformed scale (Binge eating days per week) + 1.

Secondary Endpoint(s): (if applicable)

Secondary efficacy measures include the number of Binge eating episodes per week, 1-week Binge eating episode response status, and 4-week cessation from Binge eating (free from Binge eating episodes). Other secondary endpoints include the change in weight/BMI between baseline and study endpoint, the Clinical Global Impressions–Improvement Scale (CGI-I) rated global improvement of symptoms over time (results will be dichotomized as improved [CGI-I ratings of 1 or 2 very much/much improved] or not improved [CGI-I ratings of 3-7]). The self-reported Eating Inventory, also known as the Three-Factor Eating Questionnaire, the self-reported Binge Eating Scale, the Yale-Brown Obsessive Compulsive Scale modified for Binge Eating (YBOCS-BE), the Quality of Life Inventory, the Hamilton Depression Rating Scale and the Hamilton Anxiety Rating Scale.

Study Plan:

Eighty individuals with binge eating disorder will be recruited for a double-blind, placebo-controlled pilot study in which Vortioxetine or placebo is administered in a 1:1 fashion. All 80 subjects will have binge eating disorder per DSM-5 criteria for at least a year. Following baseline measures, subjects will receive Vortioxetine (10mg for one week and then 20mg thereafter) or inactive placebo. Participants will be seen one week after the baseline visit (assessing the 10mg dose), one week after that (assessing the 20mg dose), and then every 2 weeks for the remainder of the 12-week period. At week 12, subjects will start a 1-week taper off the medication and will be seen at week 13. Efficacy and safety measures will be performed at each visit.

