
Drugs, Dosages, and Regimens

Baseline visit will consist of all evaluations. For subjects who meet inclusion/exclusion criteria, they will be randomized at the end of their baseline visit.

All 80 subjects who are randomized to Vortioxetine (1:1 randomization) will receive 10mg/day or placebo during the first week of the study (the first dose will be started the day immediately after the baseline visit). All subjects will receive 10mg or placebo for 7 days and then will be evaluated with all measures at week 1 (7 days after baseline).

At the week 1 visit, subjects will be started on 20mg/day (or remain on placebo) for the remainder of the study. They will return at week 2 (corresponding to having been on 20mg/day for one week) and be evaluated with all measures. After week 2 visit, all subjects will be seen every two weeks for the remainder of the 12-week study period (this corresponds to visits at week 4, 6, 8, 10, and 12). Week 12 evaluation will be the study endpoint for purposes of efficacy.

All visits are as outpatients and include in-person assessments.

After study conclusion (at week 12), the dose will be tapered off during a 1-week follow-up period. All subjects will return at week 13 for final safety evaluation only.

Dosage changes/reductions will not be permitted. Because nausea, and possibly headache, are the most likely side effects anticipated at the 20mg dose, participants will be allowed the use of over-the-counter options such as Tylenol prn for headaches, or bismuth subsalicylate for nausea. The use of over-the-counter options will be tracked at each visit. If side effects continue and are intolerable, the participant will have to discontinue treatment. If that occurs, a detailed 'final visit' assessment will be conducted and the participant will be contacted two weeks following to assess side effect outcomes.

Treatment Duration, Visit Frequency, and Procedures

This is a 13-week study (12 weeks of acute treatment followed by a 1-week tapering phase). Subjects will be seen for a total of 9 study visits. All visits will include the full battery of assessments except week 13 which is only a safety evaluation.

Randomization

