Participants are randomized (1:1) to receive placebo or vortioxetine by the investigational pharmacy at the University of Chicago. The study blind will be maintained by over-encapsulation, making placebo and active treatments appear identical in size, weight, shape, and color. Dosage changes and reductions will not be permitted during the study and participants will be discontinued if they experienced intolerance.

Baseline Visit Assessments

Those subjects who appear appropriate for the study, based on telephone screening, will be invited for a baseline assessment. The duration of the baseline assessment will be approximately 2-3 hours and will include the following: Informed consent, Demographic data, Concomitant medications (no psychotropic medications will be allowed), Family history data, Medical evaluation including physical examination, EKG, weight, and vital signs, Urine pregnancy test (for women of childbearing years) and urine drug screen, and a psychiatric evaluation (using the following measures: MINI International Neuropsychiatric Interview (Sheehan et al., 1998); Neurocognitive assessments of impulsivity; Depressive symptoms will be rated with the 24-item Hamilton Depression Rating Scale (HAM-D) (Hamilton, 1960); Anxiety symptoms will be assessed using the Hamilton Anxiety Rating Scale (HAM-A) (Hamilton, 1959); Psychosocial functioning will be evaluated using the patient-rated version of the

Sheehan Disability Scale (SDS) (Sheehan, 1983); Quality of Life Inventory (QOLI) (Frisch et al., 1993); Compulsivity will be assessed using the Cambridge Chicago Trait Scale (Cambridge CHI-T Scale) ([name] & Chamberlain, 2016), the Lie Acceptability Scale (Goosie, 2014), The Narcissistic Personality Inventory (Raskin & Terry, 1988), The Social Desirability Scale (Crowne & Marlowe, 1960), and the Columbia Suicide Severity Rating Scale (C-SSRS)). If subjects consent, a blood sample will be collected to check for diabetes by measuring blood glucose levels.

At baseline, binge eating will be assessed using the following: Binge eating diary, Clinical Global Impressions–Severity Scale, the Three-Factor Eating Questionnaire, Self-Reported Binge Eating Scale, and the Yale-Brown Obsessive Compulsive Scale modified for Binge Eating (YBOCS-BE). Baseline labs, as well as interim labs, may be ordered based on clinical and medical evaluation.

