Weight will be recorded using a calibrated scale with the participants not wearing shoes, rounded to the nearest 0.5 pounds, and converted to kilograms (to convert, multiply by 0.45) for data reporting.

Following-Up Visit Assessments

All follow-up visits will include safety measures (adverse events, vital signs, C-SSRS), weight, binge eating measures, Clinical Global Impressions–Improvement Scale, and other psychiatric measures.

Medical evaluation including physical examination will be performed again at study endpoint.

At study completion, participants will be made aware of all available options for follow-up care in the community.

Safety Assessments

Safety and tolerability will be assessed using spontaneously reported adverse events data, Columbia–Suicide Severity Rating Scale (C-SSRS) vital signs, and by evaluating premature termination. Safety assessments (C-SSRS, sitting blood pressure, heart rate, adverse effects, and concomitant medications) will be documented at each visit.

Subjects who are an immediate suicide risk will be removed from the study and appropriate clinical intervention (e.g. hospitalization) will be arranged. Urine pregnancy tests will be performed at the initial visit. Subjects who have a positive urine pregnancy test will be excluded from the study. Assessment of side effects will be done at each visit. AEs will be coded by system organ class (SOC) and preferred term (PT) using the Medical Dictionary for Regulatory Activities (Med- DRA) Version11.1. The incidences of all AEs will be summarized descriptively.

Safety Reporting (please do not change the safety section of the template)

Institution/Investigator is solely responsible for reporting all Adverse Events and Serious Adverse Events to regulatory authorities, investigators, IRBs or IECs and Takeda, as applicable, in accordance with national regulations in the countries where the study is conducted.

Regardless of expectedness or causality, all SAEs and pregnancy reports must also be reported in English by facsimile to Takeda Pharmacovigilance or designee:

Fatal and Life Threatening SAEs within 24 hours of the sponsor-investigator's observation or awareness of the event

All other serious (non-fatal/non-life threatening) events within 4 calendar days of the sponsor-investigator's observation or awareness of the event

Takeda Safety Reporting Contact Information

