A medication error is a preventable event that involves an identifiable patient and that leads to inappropriate medication use, which may result in patient harm. While overdoses and underdoses constitute medication errors, doses missed inadvertently by a patient do not. Individuals who identify a potential medication error situation should immediately contact Takeda (see below) and report the event.

Phone: [name] ([name])

E-mail: [contact]

[contact]

Product complaints and medication errors in and of themselves are not AEs. If a product complaint or medication error results in an SAE, an SAE form should be completed and sent to Takeda Pharmacovigilance.

Statistical Analysis:

Design/Randomization

The study is a double-blind, placebo-controlled study. Participants will be randomized (1:1) to receive vortioxetine or placebo by the University of Chicago Investigational pharmacy in block sizes of eight, using computer-generated randomization with no clinical information.

Efficacy Analysis

For statistical analysis, the full-analysis set will be defined as all participants who took at least 1 dose of the study drug and had at least 1 post-baseline primary efficacy assessment. The safety-analysis set will be defined as all randomized participants who took at least 1 dose of the study drug and completed at least 1 follow-up safety assessment.

We will compare the baseline characteristics of both groups using Fisher's exact test for categorical variables and the t test for continuous variables. We will calculate adherence to treatment, based on the number of capsules returned at each visit, as the number of capsules taken divided by the number of days in the study \times 100%.

Primary endpoint analysis

The primary outcome measure will be the change from baseline in frequency of binge eating episodes (binges/week), defined as the mean number of binges per week in 2-week intervals. If the visit interval is less than 2 weeks, the mean number of binges per week will be estimated based on the number of binge days in the interval since the last visit.

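### A fixed block size of eight stated in the protocol, and no set order between clinician efficacy ratings and side-effect review, leave two small routes around a blind that rests on capsule appearance

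*Combined protocol and SAP*

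**What the plan says.** **Blinding.** The Randomization section states: "The study blind will be maintained by over-encapsulation, making placebo and active treatments appear identical in size, weight, shape, and color". No other means of keeping the blind is described. The Study Plan makes the comparator inactive: "subjects will receive Vortioxetine (10mg for one week and then 20mg thereafter) or inactive placebo".

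**Expected side effects.** Drugs, Dosages, and Regimens explains the permitted over-the-counter remedies with "Because nausea, and possibly headache, are the most likely side effects anticipated at the 20mg dose" and adds: "The use of over-the-counter options will be tracked at each visit". All participants reach the second dose step at the week 1 visit.

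**Efficacy ratings.** Primary Endpoint(s) defines the measure as the "number of binge eating days per week based on clinician interview and confirmation of identified Binge eating episodes" recorded in a self-report diary. The CGI-I is a secondary endpoint.

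**Timing.** Safety Assessments says: "Assessment of side effects will be done at each visit". Following-Up Visit Assessments lists adverse events, binge measures and the CGI-I for every follow-up visit. Neither section says which comes first.

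**Allocation.** Under Statistical Analysis, Design/Randomization, the investigational pharmacy randomizes "in block sizes of eight, using computer-generated randomization with no clinical information". The opening table gives one site and 80 subjects, 40 per arm.

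**The concern.** Matching capsules hide what the product looks like, not what it does. Where the active arm is expected to produce a nameable effect and the placebo is inert, that effect is a cue to the arm. Under this plan the cue and the remedy taken for it can come up at the visit where a clinician decides whether a diary entry counts as a binge and scores global improvement. If the cue is heard first, it could colour the rating.

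The block size gives a second, smaller route. Staff who know that every run of eight contains four of each arm can, in principle, turn guesses about earlier participants into a guess about the next one before enrolment. That would threaten the comparability of the arms rather than the ratings.

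At stake are the CGI-I comparison most directly, the primary measure to a lesser degree because it starts from the participant's diary, and, at the margin, concealment of allocation.

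**Working it through.** The plan states no figure on this point to reproduce. The calculations below show how strong the two routes could be.

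**Inputs from the documents:** 80 participants, 1:1, 40 per arm; blocks of eight; one site; about 4 enrolled per month; significance level .05 (sidedness not stated, two-sided assumed).

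**Inputs assumed, because the documents give none:** nausea rate *a* on active and *b* on placebo; the size of any rater shift.

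**1. How well nausea reveals the arm.** A rater who guesses active when nausea is reported and placebo otherwise is right with probability ½*a* + ½(1 − *b*) = ½ + (*a* − *b*)/2. For a participant with nausea, the probability of being on active is *a*/(*a* + *b*). The share of participants with nausea is (*a* + *b*)/2.

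| *a* vs *b* | right overall | active, given nausea | share with nausea |
|---|---|---|---|
| 20% vs 15% | 52.5% | 0.20/0.35 = 57% | 17.5% |
| 30% vs 10% | 60% | 0.30/0.40 = 75% | 20% |
| 40% vs 5% | 67.5% | 0.40/0.45 = 89% | 22.5% |

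**2. Block of eight, worst case.** 80/8 = 10 blocks. If every earlier allocation in a block is known, an allocation is certain once one arm's four places are used up. The expected number of certain allocations equals the expected length of the closing run of one arm. Of the 70 possible sequences, those whose closing run is at least 1, 2, 3 or 4 long number 70, 30, 10 and 2. So (70 + 30 + 10 + 2)/70 = 1.6 per block, or 10 × 1.6 = 16 of 80 (20%).

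**3. Block of eight, cues only.** Suppose staff know not the allocations but the side-effect status of all earlier participants in the block. Weighting the 70 sequences by their likelihood, over 5,000 simulated blocks with 10% on placebo and 20%, 30%, 40% or 50% on active, the next arm is guessed correctly 51.4%, 52.5%, 53.5% or 54.5% of the time, against 50% by chance. Knowing the block size changes retrospective guesses about participants already seen by no more than 0.1 percentage point. Even this is generous: at 4 entrants per month, roughly the last two have not yet reached the week 2 visit, the first after the step to 20mg.

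**4. What a rater shift would do, if there were one.** If participants with the cue were rated *s* SD better, the spurious effect is *d* = *s*(*a* − *b*). With 40 per arm its standard error is √(2/40) = 0.224. For 30% vs 10% and *s* = 0.5, *d* = 0.10 and 0.10/0.224 = 0.447. Two-sided type I error is then 1 − Φ(1.960 − 0.447) + Φ(−1.960 − 0.447) = 0.065 + 0.008 = 7.3%. Across 20% to 50% vs 10% and *s* from 0.25 to 1.0, *d* runs from 0.025 to 0.40 and type I error from 5.1% to 43%. The width of that range shows that the documents do not fix the size.

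**The case against.** **The documents do not say that one person does both tasks, and adverse events are described as spontaneously reported.** Both points are correct. A reader might infer that a rater records nausea and then scores the CGI-I; the text does not establish that. It does require side effects to be assessed and remedy use tracked at every visit, and it neither separates the roles nor sets an order. A visit timetable is said to be attached but was not supplied, so the missing order is shown only for the text available.

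**The plan expects few side effects.** The Rationale and Sample Size sections say so. Nausea and headache are also nonspecific, and the remedies are open to both arms. This limits how many participants carry a cue. It does not remove the cue where it occurs.

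**Form order cannot protect the week 12 endpoint.** A cue heard at week 2 is still known at week 12. This stands: ordering removes only the same-visit cue. An efficacy rater who never sees adverse-event or remedy data would protect more, but needs extra staff. Neither measure helps if participants guess their own arm while keeping the diary.

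**The block argument is weak.** Largely true. A reader might take 16 of 80 as the number of allocations that would be exposed. That needs every earlier allocation to be known, while the pharmacy randomizes and nothing suggests the list is disclosed. With side-effect cues alone the gain over chance is a few percentage points.

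**This applies to most trials with an inactive placebo.** Also true. The case for change is that the two gaps cost almost nothing to close.

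**Conclusion.** The point holds as a low-cost improvement. The plan states a fixed block size in the protocol of a single-site trial, and the supplied text sets no order between clinician-judged efficacy ratings and the side-effect and remedy review. Side-effect cues **could** influence ratings, the CGI-I more than the primary measure, and could make later allocations slightly more predictable.

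A reader might go further and conclude that the primary result will be biased toward the drug, or that nausea identifies the arm with 57% to 89% certainty. The documents support neither. They give no side-effect rates and no evidence of a rater shift. The 57% to 89% applies only to the minority with nausea, under assumed rates; over all participants, the same rates give 52.5% to 67.5%. No bias estimate can be derived from the documents, and the type I error figures are conditional illustrations.

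**What to change.** 1. **Statistical Analysis, Design/Randomization:** replace fixed blocks of eight with randomly varied block sizes, generated and held only by the investigational pharmacy, and remove the block size from the protocol.
2. **Following-Up Visit Assessments:** require binge-day confirmation and the CGI-I to be completed and locked at each visit before side effects and over-the-counter remedy use are reviewed. State there that this is partial protection, since cues from earlier visits remain and participants may also guess their arm.

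**Cost:** a changed pharmacy list and a fixed form order, with no added visits or staff. Visit flow becomes slightly less flexible. If the last block is incomplete the arms may differ slightly in size, by at most half of that block's size. The content of the safety assessments is unchanged.

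A treatment-guess question, tabulated by arm, is optional. It would describe the state of the blind but would change no result, and the case for the two changes does not depend on it.

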Rationale for evaluating this compound in this population/target organ. Provide overall reason the study is being proposed, including past study results that may have led to a decision to propose this study.

Vortioxetine has distinctive properties that make it a promising option for patients with

binge eating disorder. In vitro studies indicate that vortioxetine is an inhibitor of the 5-HT transporter and is a 5-HT1D, 5-HT3 and 5-HT7 receptor antagonist, a 5-HT1A receptor agonist and a 5-HT1B receptor partial agonist. Animal and in vitro studies indicate that several neurotransmitter systems may be impacted by vortioxetine, with the drug enhancing levels of 5-HT, noradrenaline, dopamine, acetylcholine and histamine in certain areas of the brain, as well as modulating γ -aminobutyric acid and glutamate neurotransmission (Gibb and Deeks, 2014). In addition, vortioxetine appears to improve executive functioning which in turn has the potential to improve top-down cognitive control (Mahableshwarkar et al., 2015). This suggests that vortioxetine could improve the symptoms of binge eating disorder by two complementary pathways. Finally, because of low rates of side effects, low likelihood of sexual dysfunction, and the potential for improved cognitive performance, vortioxetine should be a well-tolerated and in fact desired medication approach to binge eating.

Given the serious public health problems associated with binge eating disorder, and the likelihood of success of vortioxetine in treating the disorder, the aim of the present study was to examine the efficacy and safety of vortioxetine vs placebo in adults with moderate to severe Binge eating disorder, as indicated by at least 3 binge eating days per week for the 2 weeks before the baseline visit

Hypothesis:

State hypothesis for study objectives.

We hypothesize that vortioxetine will be more effective than placebo in reducing the number of binge eating days per week after 12 weeks of treatment when compared to baseline.

Primary Aim/Objective:

For clinical studies– eg, To evaluate the safety and efficacy of interventions with test medication on symptoms, signs and quality of life in patients with target condition.

The aim of the present study is to examine the efficacy and safety of vortioxetine vs placebo in adults with moderate to severe Binge eating disorder, as indicated by at least 3 binge eating days per week for the 2 weeks before the baseline visit.

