Between group comparisons will use a mixed-effects model for repeated measures, including fixed factors for treatment and visit, the interaction of treatment and visit, a covariate of the log-transformation ([baseline number of BE days per week] + 1), and the interaction of the baseline covariate and visit using visit as a categorical variable. Mixed-effects models for repeated measures estimates differences from placebo in the change from baseline of the log-transformed scale ([BE days per week] + 1) at week 12 (primary end point). Based on previous research, log-transformation should reduce skewness (McElroy et al., 2007).

Secondary endpoints analyses

Secondary outcome measures will include the change from baseline in frequency of binge days (or mean days per week when the participant had one or more binges), weight, body mass index, global improvement, Three-Factor Eating Questionnaire, and Impact of Weight on Quality of Life.

We will also analyze changes from baseline in log-transformed BE episodes, TFEQ factor scores, and YBOCS-BE total score to week 12 using the mixed-effects model for repeated measures. Pairwise χ^2 statistical tests will evaluate dichotomized CGI-I ratings at week 12 for placebo vs treatment group.

Response categories will be tabulated based on the percentage decrease in frequency of binges from baseline to endpoint, which will be defined as follows: complete=cessation of binges; marked=75% to <100% decrease; moderate=50% to <75% decrease; and none=<50% decrease.

We will calculate effect sizes for the primary analysis of binges per week and weight using Cohen's d. Finally, we will perform a Spearman rank correlation to assess the association between the change in frequency of binges from baseline to week 12 and the change in weight from baseline using completers.

Safety analyses

Adverse events will be collected at baseline visit. We will evaluate differences between groups in the incidence of treatment-emergent adverse events using Fisher's exact test. Descriptive statistics will be used to evaluate changes in laboratory values, blood pressure and heart rate.

Sample Size

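### The adverse event collection method is described inconsistently and the only one named is passive; a scripted enquiry at every visit would be a cheap improvement

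*Combined protocol and SAP*

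**What the plan says.** The Primary Aim puts safety beside efficacy: "The aim of the present study is to examine the efficacy and safety of vortioxetine vs placebo in adults". The Primary Endpoint and the Sample Size sections concern efficacy only.

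The combined protocol and SAP describes adverse event collection in several places:

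- **Safety Assessments**, opening sentence: "Safety and tolerability will be assessed using spontaneously reported adverse events data". The sentence goes on to list the C-SSRS, "vital signs, and by evaluating premature termination".
- **Safety Assessments**, next sentence: "Safety assessments (C-SSRS, sitting blood pressure, heart rate, adverse effects, and concomitant medications) will be documented at each visit".
- **Safety Assessments**, later: "Assessment of side effects will be done at each visit".
- **Following-Up Visit Assessments**: adverse events are among the safety measures at all follow-up visits.
- **Drugs, Dosages, and Regimens**: nausea and possibly headache are the side effects thought most likely. Of their non-prescription remedies it says "The use of over-the-counter options will be tracked at each visit". A participant who stops for intolerance has a final assessment and a contact two weeks later.
- **Safety analyses**: the one statement on collection names the baseline visit. The analysis is then given: "We will evaluate differences between groups in the incidence of treatment-emergent adverse events", by Fisher's exact test.

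The Rationale expects good tolerability "because of low rates of side effects, low likelihood of sexual dysfunction, and the potential for improved cognitive performance". The Sample Size section uses low adverse event rates and the sexual side-effect profile to argue for few drop-outs.

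**The concern.** Someone running a visit cannot tell from these sections whether to ask about symptoms, and in what words, or to wait to be told. The only method with a name is spontaneous reporting.

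If that is what happens in practice, the incidence of ordinary symptoms will be under-counted, and not evenly. Nausea and headache have an indirect prompt, because use of their remedies is tracked. Suicidality has its own scale. Sexual dysfunction has neither. A low count for it could reflect the drug or the absence of a question, and the trial report could not separate the two. That matters because low rates of side effects and of sexual dysfunction are premises of the study. Answers that were never collected cannot be recovered at analysis.

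**Working it through.** **1. What each safety source can detect.** The documents give no adverse event rate, reporting fraction or safety sample size, so there is no stated figure to reproduce. The first check sets the sources side by side.

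| Source | Depends on volunteered reports? | Detects symptoms short of drop-out? |
|---|---|---|
| C-SSRS | No | Suicidality only |
| Vital signs | No | No |
| Premature termination | No | No, by definition |
| Tracking of over-the-counter remedies | No | Indirectly, for nausea and headache |
| Adverse event record | Not settled by the text | Yes |

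For ordinary symptoms the adverse event record is the main source, and it supplies the incidences that are tested.

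**2. What incomplete capture would do.** The following are assumptions, not figures from the documents: true incidence 30% on drug and 8% on placebo, and a share *f* of affected participants recorded, the same in both arms. The 40 per arm is from the Sample Size section. The test is Fisher's exact, two-sided at 0.05 (the protocol does not state sidedness).

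- Recorded rates are 0.30*f* and 0.08*f*.
- Recorded difference is 0.22*f*.
- Recorded ratio is 0.30*f* / 0.08*f* = 3.75 for every *f*.
- Power is the summed probability, over all pairs of binomial counts, of those giving p ≤ 0.05.
- For an effect with true incidence 10% on drug, the chance of recording no case among 40 is (1 − 0.10*f*)^40.

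| *f* | Recorded rates | Difference (points) | Power | No case in 40 at 10% true incidence |
|---|---|---|---|---|
| 1.0 | 30% vs 8% | 22 | 65% | 1.5% |
| 0.9 | 27% vs 7.2% | 19.8 | 58% | 2.3% |
| 0.8 | 24% vs 6.4% | 17.6 | 51% | 3.6% |
| 0.5 | 15% vs 4% | 11 | 23% | 13% |
| 0.3 | 9% vs 2.4% | 6.6 | 7% | 30% |

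Other assumed rates give the same pattern. With 30% against 10%, power is 53% at full capture, 37% at 75%, 18% at 50% and 3% at 25%.

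**3. What prompting could cost.** Suppose yes/no items capture everything but also bring in an independent 10% of background complaints in each arm, and the two are pooled. The rates become 1 − 0.70 × 0.90 = 37% and 1 − 0.92 × 0.90 = 17.2%, and power is 43%. That is below the 65% for full capture without noise, and below the 51% for 80% capture. Prompted and unprompted events should therefore not be merged.

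**The case against.** The strongest objection is that the plan does more than the words on spontaneous reports suggest. The same sentence lists three other measures, and premature termination bears directly on tolerability. Adverse effects are documented and side effects assessed at each visit, and there is a physical examination at study endpoint. Spontaneous reporting is not defined; it may mean only that no checklist is used, which fits recording at every visit. All of this stands. The statements in Safety Assessments are therefore not a strict contradiction; what is missing is a defined enquiry.

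It is also fair that the rates and capture fractions above are assumed, that mild under-capture costs much less than severe, and that even full capture gives only 65% power, so part of the limitation is 40 per arm. Severe under-capture is least plausible for nausea and headache.

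On sexual dysfunction, the Hamilton scales are administered, but their items are not reproduced in the protocol and nothing routes them into adverse event data. The visit timetable is described as attached and is not in the supplied text. The statement must therefore be limited to no enquiry being stated in that text.

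A reader might infer that safety rests on volunteered reports alone, or that the trial could not show anything but good tolerability. The documents do not support either. The first ignores the other measures and the visit-by-visit assessment. The second fails on the illustration itself: at 50% capture an effect with 10% true incidence is still recorded at least once with probability 87% (1 − 0.129), and equal under-capture leaves the rate ratio intact.

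**Conclusion.** The point holds as a cheap improvement. The method of adverse event collection is described inconsistently, no elicitation question is given, and the only method named is passive. The incidences compared by Fisher's exact test may therefore be too low and uneven across symptoms, with sexual dysfunction the clearest gap.

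The size of any under-count cannot be derived from the documents. Under the assumed 30% against 8%, power falls from 65% to between 58% (90% captured) and 7% (30% captured). Equal capture in the two arms shrinks the absolute difference and the power but not the ratio. The direction follows only if events are in practice left to be volunteered, which the text leaves open.

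The primary efficacy endpoint and its analysis are unaffected.

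**What to change.** Reconcile Safety Assessments with Safety analyses so that both state one method:

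1. Ask the same scripted open question, in both arms, at baseline and at every follow-up visit.
2. Follow it with yes/no items for the effects the protocol itself names: nausea, headache and sexual dysfunction.
3. Count an event as treatment-emergent only if it is new or worse than the baseline answer. This agrees with the existing adverse event definition, which covers new events and earlier conditions that have increased in severity or frequency.
4. Tabulate and test volunteered or open-question events separately from prompted ones.

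The cost is revised wording in two sections, a one-page form and a few minutes at visits already scheduled. No new visit, staff or sample size is needed. The drawback is that more mild background events will be recorded in both arms, which would dilute the comparison if the two kinds were pooled. Separate tables avoid this and keep a count that can be set beside studies using spontaneous reports.
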